6.2.4 Contamination

Since the study is not necessarily blind to participants, we will take steps to evaluate potential contamination with regard to the intervention by way of communication among women who may receive services in the same setting. It is possible that participants that receive MMORE will interact with women in the TAU only group through the partner practice and communicate about the intervention. While it is unlikely that communication will convey substantive information to influence results, we will evaluate extent of potential contamination by including questions about communication with others about the intervention in the post-intervention assessment battery (e.g. Did you talk with other women in the study? What information conveyed? What information learned?).

6.2.5 Follow-up Visit

All study participants will be followed until 3 months postpartum.

6.2.6 Completion/Final Evaluation

The study team will evaluate intervention implementation outcomes at each of the partner practices to inform exploratory Aim 3 goals of the MMORE intervention at partner practices. In addition to summative indicators of intervention acceptance, feasibility, fidelity, and reach, practice stakeholders will complete indicators of Readiness to Implement Change and Program Sustainability. Descriptive statistics will be used to identify key facilitators to sustained implementation of the intervention.

7. SAFETY ASSESSMENTS

7.1 Specification of Safety Parameters

Procedures to Ensure Safety: All participants will be informed that information obtained through activities is confidential and that they can choose not to answer certain questions. All audio recordings of interviews will be destroyed after transcription. All potential risks associated with participation in this study will be disclosed in consent documents. As in other studies with this population, we have obtained a waiver of signed consent for study activities.

Procedures for minimizing risk to physical health from yoga practices.

Intervention Instructors will complete the Session Event Checklist after each intervention session to denote any adverse events (non-serious and serious) that take place during the intervention sessions. Participants will complete the Intervention Experience Form at the end of each session to document experience of any adverse events including physical experiences (e.g., shortness of breath, pain, increased or decreased infant movement, or other discomfort experiences during the session) and psychological experiences (e.g., emotional flooding, uncontrollable crying). At the end of each intervention week, all participants will also complete a Weekly Monitoring Form that will include items related to any additional experience of adverse physical or psychological events. The lead project coordinator will administer the Weekly Monitoring Form by telephone or e-mail.

Intervention sessions will be conducted at the partner practice. In the event of an adverse physical health event occurring during an intervention session or during the study period outside of intervention session, the instructor and study team member will follow the best practice procedures of the partner practice. Risks associated with physical health will be overseen by Drs. [name], [name] and [name].

The events will be reported, monitored and tracked as outlined in the DSMP.

Procedures for managing suicide ideation or other mental health conditions

As with other interventions, yoga and other mindfulness interventions can elicit feelings for some participants that are uncomfortable. The safety checklists described above will include items related to the experience by participants of emotions or feelings, from quiet tears to sobbing. The experienced Lead yoga instructors in this project are seasoned in supporting clients in managing of feelings so that they do not become overwhelming. The Lead Instructor has worked with vulnerable populations like those in the proposed study, including women with significant trauma histories and involvement in the criminal justice system.

In the unlikely event that participants indicate either during the intervention or in the assessment that they have feelings of hurting themselves or others, the intervention instructor and study team will follow the best practice procedures of the partner practice and the participant will be provided with appropriate referral to treatment and resources. Risks associated with mental health conditions will be overseen by Drs. [name] and [name].

The events will be reported, monitored and tracked as outlined in the DSMP.

Procedures for managing relapse.

In the event that a study participant lapses or relapses during the study period, cases will be handled on an individual basis, which will be largely determined by the procedures of the partner maternity care practice in terms of preference for ongoing care. A lapse/relapse will not necessarily lead to participant discontinuation in the study.

The lead instructor is trained to manage such instances and the safety protocol to be followed by the instructor and study team will include procedures consistent with partner practices to address situations where discomfort requires a higher level of attention. If a participant is deemed to be impaired at an intervention session such that she is disruptive to the group or presents as a safety hazard to others, the study team member will follow partner practice best practice to work with the participant to leave the room.

Risks associated with substance use and relapse will be overseen by Drs. [name], [name] and [name].

Other procedures to ensure safety, privacy and confidentiality of participants

All efforts will be made to encourage trust and respect among participants in the group sessions and to ensure that information disclosed remains confidential. Any recordings of sessions will use processes to de-identify individual participants. All recordings will be destroyed at the end of the study after processing.

Protection of risks associated with use of a computer or mobile phone to complete research activities. All efforts will be made to ensure data security while utilizing Zoom for the virtual intervention. End-to-end encryption settings will be enabled for an added layer of application security in addition to being password protected with ‘waiting rooms’ enabled, in-progress meetings being locked, and enabling the removal of attendees. The greatest risk with using any virtual platform is entry of

someone other than designated study participants. The Dartmouth institutional Zoom has a number of protections in place, including study staff control of who enters the intervention space (via waiting room and specific participant codes). Per Zoom documentation: “Meeting hosts can enable the end-to-end encryption setting to their meetings for an added layer of application security. Enabling this setting will force encryption across Zoom running on desktop, mobile and Zoom Rooms, as well as for H.323/SIP endpoints except PSTN telephone. It will also force end-to-end group messaging (chats). Dartmouth ITC Security recommends that meeting hosts enable the added layer of end-to-end security for meetings where highly-confidential or regulated information, such as PHI, HIPAA, PII, or FERPA data may be exchanged or discussed.” We will be working with Dartmouth ITC to ensure our Zoom platform for virtual delivery is maximally secured technologically.

Participant access to assessment surveys will require unique user login and password, and loss of passwords will require double authentication. Other steps to protect confidentiality include: 1) Mobile phones used in the study will be required to have passcodes to help protect from unauthorized access to the application, 2) Assessment data will be encrypted and secured thus mitigating or reducing the risk of data loss during the transmission process, and 3) Access to the digital support resources of the intervention will also require a unique username and password.

Participants will be instructed that their responses to assessment surveys are voluntary and that they can decline to answer any questions that they choose. They will be assured that participation will not affect their access to treatment or perinatal care in any way.

All data collected will be housed on a secure, encrypted server protected behind firewalls and located in a secured location under 24/7 surveillance. The study team uses state-of-the-field Transport Layer Security (TLS) encryption to prevent eavesdropping and tampering of data while it is in the transmission pipeline. All research assessment data will be stored in secure databases that will not directly link participant data with identifying participant records. A separate, secure database of study participants contact information will be created to assure intervention delivery to enrolled participants and to maximize security. All possible safeguards will be taken to prevent disclosure of personal information; communication of identifiable sensitive personal information via text messages will be avoided. Participants will be instructed not to share their mobile phones.

Confidentiality training will be required for all new employees and project members and refresher seminars annually for all employees. All research staff will fulfill the educational requirements set forth by the Office for Human Research Protections at Dartmouth College. Data for all participants will be kept strictly confidential, except as mandated by law. We have received a Certificate of Confidentiality for the study to further protect participants. Paper documentation will be kept in locked file cabinets located in a locked study team office. All data presentation will be of aggregate-level data; participants are never individually named.

7.2 Methods and Timing for Assessing, Recording, and Analyzing Safety Parameters

Safety parameters will be assessed by the methods described above and in the DSMP, including the checklist forms and study team member progress notes. The study team will review safety parameters weekly during the course of the intervention. Events will be summarized and provided in a report

provided to the Independent Monitoring Committee. The summary reports will also be reviewed by the SAC.

7.3 Adverse Events and Serious Adverse Events

The potential for unexpected events in this study is minimal. The primary unexpected event may be discomfort when completing assessments that include measures about substance use, stress and mental health, parenting, and recovery. As noted previously, we will take precautions to ensure messages for participants to reinforce the confidentiality of assessment survey, and intervention that participants can take as many breaks as needed when completing study activities. Any other unexpected or adverse events will be handled according to the policies and procedures at our community partners' facilities. These procedures will be summarized and provided to participants at the time of consent.

An **adverse event (AE)** is generally defined as any unfavorable and unintended diagnosis, symptom, sign (including an abnormal laboratory finding), syndrome or disease which either occurs during the study, having been absent at baseline, or if present at baseline, appears to worsen. Adverse events are to be recorded regardless of their relationship to the study intervention.

A **serious adverse event (SAE)** is generally defined as any untoward medical occurrence that results in death, is life threatening, requires inpatient hospitalization or prolongation of existing hospitalization, results in persistent or significant disability/incapacity, or is a congenital anomaly.

7.4 Reporting Procedures

SAEs that are unanticipated, serious, and possibly related to the study intervention will be reported to the Independent Safety Monitor(s), IRB, and NCCIH in accordance with requirements.

- Unexpected fatal or life-threatening AEs related to the intervention will be reported to the NCCIH Program Officer, and Independent Safety Monitor(s) within 3 days of the investigator becoming aware of the event. Other serious and unexpected AEs related to the intervention will be reported within 7 days.
- Anticipated or unrelated SAEs will be handled in a less urgent manner but will be reported to the Independent Safety Monitor(s), IRB, and other oversight organizations in accordance with their requirements. and will be reported to NCCIH on an annual basis.
- All other AEs documented during the course of the trial will be reported to NCCIH on a quarterly basis by way of inclusion in the reports provided to NCCIH and to the Independent Monitors. The Independent Safety Monitor(s) Report will state that all AEs have been reviewed.

The Contact PI will be responsible for determining whether an SAE is expected or unexpected and related to the intervention. An adverse event will be considered unexpected if the nature, severity, or frequency of the event is not consistent with the risk information previously described for the intervention.

The details of reporting and follow-up for adverse events are included in the **Data Safety and Monitoring Plan** for the study.

7.5 Follow-up for Adverse Events

All Adverse Events will be followed in timely manner and consistent with the standard procedures of

our partner practices. AE will be followed for 7 days following the completion of the study period. SAE will be followed for 30 days following completion of the study period.

7.6 Safety Monitoring

The NCCIH requires that all Human Subjects research studies undergo independent monitoring, and NCCIH Program Officials will provide specific guidelines to the PI for the study.

We have identified three independent monitors for the R33 study and their materials have been provided to the study Project Official.

The following safety characteristics will be tabulated monthly and reported to the Independent Study Committee quarterly.

1. Non-serious and serious adverse events, as documented in the Session Event Forms, Intervention Experience Forms, the Weekly Monitoring Forms, and study team member progress notes during intervention sessions. These include physical side effects of the intervention or injuries occurring in class or during home practice.
2. Any other unrelated, possibly related, and related adverse events reported by participants
3. Attribution of adverse event to the study intervention, determination of whether the adverse event was expected or unexpected, and resolution or study adjustments, as necessary

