Early postpartum period presents increased risk for MOUD discontinuation. Even when treatment is initiated, there is a high rate of discontinuation, particularly during the early postpartum period. In a recent systematic review, prenatal discontinuation rates ranged from 0-33%, and postnatal rates from 26-64%. In a well-established integrated perinatal obstetric-MOUD program in NH, MOUD discontinuation was 40% at 3 months postpartum, with the greatest drop-off evident between 6 weeks and 3 months postpartum. Much of the extant literature focuses on methadone discontinuation and there is a need for research on treatment retention among women receiving buprenorphine, particularly during the early postpartum period. The proposed project aims to address this research gap.

Pain management is complicated for pregnant and parenting women with OUD. Pain management, already a common concern for intrapartum and postpartum care, is complicated in the context of opioid dependence. In addition to natural pregnancy-related pain (e.g., leg and lower back pain, musculoskeletal pain), chronic pain (e.g., endometriosis, traumatic injury) is often part of the clinical portrait of women with substance use disorders. The limited literature regarding perinatal pain management for women with OUD indicates that pregnant women on MOUD can experience cross-tolerance for other pain medications, requiring more medication to manage pain. Increased sensitivity to pain (hyperalgesia) is also a hallmark of long-term opioid use, also necessitating use of more intensive pain management strategies. Mental health conditions can exacerbate patients' experiences of pain, and sleep quality, a critical component of wellbeing, is negatively affected by pregnancy and opioid dependence. Poor sleep quality is associated with increased sensitivity to pain and is a risk factor for relapse. Several studies suggest that pain management for women with OUD deteriorates postpartum, such that women on MOUD experienced increased pain postpartum compared with opioid-naïve women. Under-treatment of pain can significantly increase risk of relapse. Accessible non-pharmacological approaches to pain management may offer an important adjunct to recovery support for pregnant and parenting women with OUD.

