6.2 Description of Evaluations

Outcomes. Participant outcomes will be assessed by way of clinical record review of consented participants and participant self-report. Implementation outcomes will be assessed through intervention usage data, and quantitative and qualitative methods.

Clinical Record Data Collection Procedures: The trained lead project coordinator will conduct chart reviews using approved data collection procedures the research team has used in other studies with this target population. Chart reviews will be conducted at intervals corresponding to 3 months postpartum for participants.

As used in other approved studies conducted by the study team, the research team will work with each practice partner to identify the best strategy for conducting chart review for consented study participants. The practice will provide the identified record list and the lead project coordinator will create a master-code that includes only the respective record numbers and unique study IDs. The master-code will be stored in separate, secured location at the respective partner practice and will only be referred to by the research team for the purposes data quality to ensure completeness of the research database.

The lead project coordinator will collect the chart data using a REDCap Clinical Data Collection template that includes only the corresponding unique study ID. All chart review data collection will occur at the partner practice location and the de-identified research data will be stored on the secured, HIPAA-compliant Dartmouth College REDCap server.

The master-code will be the only linkage between the unique study identifiers contained in the database and the patient record identifier. Upon completion of all data collection and analyses, the master-code will be destroyed so there will be no link to identifiable records in the study. We will not collect any individual identifiers as part of the research database. The single source of PHI (MRN) will be associated only with the unique study ID in the master-code. The PHI will be accessible only to the principal investigator and authorized study staff. The PHI will not be disclosed to any other person or entity.

Clinical Record Data Indicators. The following assessment metrics will be collected from clinical records of consented participants:

Primary End Points:

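### The adverse-event sources named in 7.6 stop with the intervention weeks and are unequal by arm, no method is stated for finding events at Post or 3 months postpartum, and the planned chart review has no safety field

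*Combined protocol and SAP*

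**What the plan says.** **Scope.** Section 7.3 sets a wide duty: "Adverse events are to be recorded regardless of their relationship to the study intervention". Its definition of a serious event includes death, inpatient admission and congenital anomaly. Section 6.2.5 follows all women to 3 months postpartum, and 7.5 follows serious events for 30 days beyond the study period.

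**Sources.** Section 7.6 item 1 covers events "as documented in the Session Event Forms, Intervention Experience Forms, the Weekly Monitoring Forms, and study team member progress notes during intervention sessions". Item 2 adds "Any other unrelated, possibly related, and related adverse events reported by participants", with no instrument or time limit. On timing, 7.1 says "Intervention Instructors will complete the Session Event Checklist after each intervention session" and "At the end of each intervention week, all participants will also complete a Weekly Monitoring Form"; the Intervention Experience Form is also completed at the end of each session. Section 7.2 adds: "The study team will review safety parameters weekly during the course of the intervention".

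**Later time points.** The 6.1 schedule marks Adverse Events during the intervention, at Post and at 3 months postpartum. Section 10.1 lists an Adverse Events case report form, separate from the session and weekly forms, without stating its source or timing. The survey contents described in 6.2 include no AE item.

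**Chart review.** Section 6.2 says "Chart reviews will be conducted at intervals corresponding to 3 months postpartum for participants". The indicators listed are MOUD retention, opioid abstinence and other substance use.

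**Deferred detail.** Sections 7.1, 7.2 and 7.4 refer part of the safety method to the DSMP, which is not among the supplied documents.

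**The concern.** The recording duty lasts longer than the stated means of meeting it. Once the intervention weeks end, the only route that 7.6 names is for the woman to come forward. A woman who has died cannot do so, and one who is lost to follow-up may not. The background section itself cites overdose deaths, prematurity and low birth weight in this population, so such events are foreseeable. The expedited clocks in 7.4 run from the investigator's awareness of an event, so an undetected event never starts them.

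The second problem is comparability. Session checklists, experience forms and session notes cannot exist for a woman on treatment as usual. A comparison of event counts by arm would therefore partly reflect how often, and by whom, events were looked for.

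**Working it through.** The plan gives no figure for this point, so there is none to reproduce. The check has three parts.

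**1. Coverage by source, as written**

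| Source | When | Arms |
|---|---|---|
| Session event form or checklist | each session | MMORE only |
| Intervention Experience Form | each session | MMORE only |
| Session progress notes | each session | MMORE only |
| Weekly Monitoring Form | each intervention week | all participants, as worded |
| Participant report (7.6 item 2) | not stated | both |
| Adverse Events form (10.1) | not stated | not stated |
| Chart review (6.2) | 3 months postpartum | both, but no safety field listed |

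With 8 sessions, a woman in the MMORE arm has up to 8 × 1 = 8 Intervention Experience Forms for which a woman on treatment as usual has no counterpart.

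**2. Follow-up time after the forms stop**

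Inputs from the documents:
- Entry is aimed at the second or early third trimester (section 3).
- The course is 8 sessions over 10 weeks (5.1). Section 3 puts the post-intervention assessment at 8 weeks for treatment as usual, so D = 8 or 10.
- A new group starts at least every 8 weeks (6.2.2), from which a wait of L = 0 to 8 weeks is inferred.

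Assumptions not in the documents: entry week E between 14 and 30, birth week B of 37 or 40, and 3 months taken as 13 weeks.

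- Forms stop at week E + L + D.
- Weeks left = (B + 13) − (E + L + D).
- Share = weeks left / (B + 13 − E).

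| B | E | L | D | Forms stop | Weeks left / follow-up | Share |
|---|---|---|---|---|---|---|
| 40 | 14 | 0 | 8 | 22 | 31/39 | 79% |
| 40 | 20 | 0 | 10 | 30 | 23/33 | 70% |
| 40 | 24 | 0 | 10 | 34 | 19/29 | 66% |
| 40 | 28 | 0 | 10 | 38 | 15/25 | 60% |
| 40 | 20 | 8 | 10 | 38 | 15/33 | 45% |
| 40 | 28 | 8 | 10 | 46 | 7/25 | 28% |
| 37 | 30 | 8 | 10 | 48 | 2/20 | 10% |

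The first and last rows are the extremes of the scenarios examined. In the last two rows the forms run 46 − 40 = 6 and 48 − 37 = 11 weeks past birth. With no wait, the most postpartum coverage arises at B = 37, E = 30, D = 10: forms stop at week 40, covering 3 of 13 postpartum weeks and leaving 10. Every scenario leaves at least 2 weeks before the 3-month point.

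**3. Women who may give no later report**

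Section 9.2 allows for 20% attrition: 0.20 × 150 = 30 women. This is a planning allowance for the whole sample, not a forecast of missed events.

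**The case against.** The strongest reply is that the plan does intend safety data after the sessions. The schedule marks AEs at both later time points, a dedicated Adverse Events form exists, 7.1 refers to events outside sessions, and 7.5 follows events beyond the study period. The survey and chart lists in 6.2 describe endpoints, so the absence of AE items there is weak evidence. The DSMP may hold the method. This reply stands against any claim that AE collection ceases. It does not supply a detection method: a form records an event once it is known, and 7.2 illustrates the methods only with checklists and progress notes.

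Several stronger readings are tempting but unsupported:

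- That postpartum serious events surface only if the woman reports them. This cannot be confirmed without the DSMP.
- That the protocol calls the postpartum window highest-risk for serious events. Section 2.1 speaks of MOUD discontinuation, "with the greatest drop-off evident between 6 weeks and 3 months postpartum", which is an efficacy matter.
- That loss to follow-up will differ by arm because retention is expected to. The difference assumed in 9.2 is in MOUD treatment retention; the attrition allowance is not split by arm.
- That most serious events fall after the forms stop. The shares above are calendar time, and the documents do not give the timing of such events. For late entrants birth can fall inside the course.
- That a woman who was admitted cannot report it. She can, at a later survey, if asked.

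The limits of chart review also stand. It takes place at the partner practice, infant findings may lie outside the mother's record, and 6.2.3 lists the lead project coordinator, who abstracts the charts, as un-blinded.

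**Conclusion.** The point holds on the supplied text. Every source in 7.6 item 1 ends with the sessions or intervention weeks, three of the four exist only in the MMORE arm, and the later AE marks in 6.1 have no stated means of detection. The one planned data source that reaches both arms without depending on the woman's report carries no listed safety field. Between about 10% and 79% of follow-up time lies after the forms stop; the width of that range comes from the assumed entry week, wait, course length and birth week.

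Followed as written, the plan could miss serious events in women who die or are lost to follow-up, and it would ascertain events unequally by arm. It does not show that postpartum events would go unobserved, because the DSMP may add sources. If it does, much of the correction is alignment of text. The change is worth making because a better source is already in use.

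**What to change.** - **7.6:** name chart review as a safety source for both arms.
- **Chart template:** add dated fields to the existing REDCap template, covering randomization to 3 months postpartum, for maternal death; hospital admission other than for uncomplicated birth; overdose; pregnancy loss or preterm birth; and infant congenital anomaly where it is documented in the mother's record.
- **Adverse Events form:** state its source and timing at Post and 3 months postpartum, for example a short event list in those two surveys, identical in both arms.
- **7.2:** extend the safety review to the end of follow-up.
- **Consistency:** align 6.1, 7.2, 7.6 and the DSMP.
- **Reporting:** tabulate these events by arm, separately from events found only through session forms.

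**Cost.** Abstraction takes slightly longer per chart, more serious events will be recorded, and consent wording may need a change. No extra visit is needed. Events treated elsewhere may still be missed, and those found at the 3-month chart review will be detected late, so chart review supplements prompt reporting and does not replace it. Dated, objective fields limit the effect of an un-blinded abstractor but do not remove it.
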